Appendix I - Consent Form

Appendix II – Patient Medication Diary

Appendix III – The Low Iodine Diet

Appendix IV –Guidance for Management and Investigation of Selumetinib Related Adverse Events

**Schema**

\*Observation time points: 1 and 3 months post-treatment, followed by every 3 months for 12 months post-treatment, followed by every 6 months for a maximum of 2 years from randomization.

\*\*Can be given up to 8 weeks (i.e. the time on treatment including treatment interruptions) (see section 7)

Generic name: Selumetinib Brand name(s): ACCRU Abbreviation: AZD6244 Availability: AstraZeneca	Generic name: Placebo Brand name(s): ACCRU Abbreviation: PLACEB Availability: AstraZeneca
---	--

## 1.0 Background

*Utility of I therapy for radioiodine-avid thyroid cancers:* The majority of thyroid cancers are differentiated carcinomas of follicular origin with papillary thyroid cancer (PTC) being the most common followed by follicular thyroid cancer (FTC) (use of the term “thyroid cancer” in this protocol refers specifically to follicular cell derived thyroid malignancies). Metastatic disease represents the most frequent cause of thyroid cancer-related death (Mazzaferri and Kloos, 2001). Since the ability to transport iodide is retained in thyroid carcinomas of follicular origin and is restricted to only a few cell types, radioactive iodine (RAI or I) can be used therapeutically to deliver tumoricidal doses of radiation, eliciting clinical benefit with few side effects and modest long-term toxicity.

I can be particularly effective for small volume (<1 cm), RAI-avid (RAIA; tumors with detectable RAI uptake) disease with complete remission achieved in reportedly over 50% of patients (Durante et al., 2006). However, I efficacy is significantly lower for patients with larger, structurally evident disease. Sabra et al. published a retrospective study evaluating the efficacy of first-line I therapy (RAI administered for remnant ablation and evidence of RAIA distant metastasis on post-ablation scan) for patients with metastatic, RAIA thyroid cancer. In 36 patients with structural disease, the response rate of metastatic lesion(s) to initial RAI ablation therapy was 22% (Sabra et al., 2013). This observation is consistent with the 10% to 24% response rates reported in other retrospective series for similar subsets of patients (Durante et al., 2006; Klubo-Gwiezdzinska et al., 2011a; Klubo-Gwiezdzinska et al., 2011b; Tala et al., 2011).

I efficacy against thyroid metastases is determined by the I activity that can be successfully delivered to metastatic lesions (Dorn et al., 2003; Maxon et al., 1992; Maxon et al., 1983; Thomas et al., 1976). Both I uptake and retention can be impaired by diminished expression of several thyroid-specific genes, including the sodium iodide symporter (NIS; mediates iodide uptake into thyroid cells) and thyroperoxidase (TPO; critical for iodide retention). Many investigators have searched for drugs to “re-differentiate” metastatic thyroid cancers to restore expression of these genes in an attempt to enhance I delivery and efficacy. Unfortunately, such studies have historically reported only modest effects upon I action.

*Thyroid cancer mutations that activate the MAPK pathway de-differentiate thyroid cancer cells:*

Mutually exclusive genetic alterations in the growth factor receptor *RET*, the three isoforms of *RAS* (*N*, *H*, *K*), and *BRAF* are present in ~70% of PTCs (Cohen et al., 2003; Kimura et al., 2003; Knauf and Fagin, 2009; Soares et al., 2003). These oncoproteins participate in MAPK signaling to activate downstream kinases MEK and ERK (RET->RAS->RAF->MEK->ERK). The *BRAFV600E* mutation is the most common genetic alteration in PTC (involving about 45% of tumors) (Kimura et al., 2003; Ricarte-Filho et al., 2009). *BRAF* MUT tumors have a more aggressive clinical behavior and are prone to being RAI-refractory (Elisei et al., 2008; Lee et al., 2007). Beyond promoting cellular proliferation and survival, *BRAF* mutations in thyroid cancer have also been implicated in disrupting follicular cell differentiation, including the suppression of key genes involved in iodide metabolism (Durante et al., 2007; Liu et al., 2007; Riesco-Eizaguirre et al., 2006) and iodide uptake, such as *NIS* (Riesco-Eizaguirre et al., 2006). In rat thyroid PCCL3 cells with inducible expression of *BRAFV600E*, treatment with the MEK inhibitor U0126 restored expression of *NIS* as well as thyroid stimulating hormone (TSH) receptor and thyroglobulin (Liu et al., 2007).

Other MAPK activating alterations common to thyroid cancer can also cause de-differentiation. *RAS* mutations are found in approximately 10-20% of PTCs and 40-50% of FTCs (Nikiforov and Nikiforova, 2011). Recombination events that lead to the fusion of the *RET* tyrosine kinase receptor with one of several partner genes (known as *RET/PTC* rearrangements) occur in 10-20% of PTCs (Nikiforov and Nikiforova, 2011; Soares et al., 2003; Zhu et al., 2006). Overexpression of either the *HRASV12* mutant or *RET/PTC* in thyroid cancer cells suppresses *NIS* expression, which can be restored with MEK inhibitor

treatment (De Vita et al., 2005; Knauf et al., 2003). Hence, genetic alterations that account for MAPK activation in the vast majority of thyroid cancers can promote MEK-dependent *NIS* suppression, diminished iodide avidity, and resistance to  $^{131}\text{I}$  therapy.

**MAPK pathway inhibition can restore iodide incorporation in an in vivo thyroid cancer animal model:** In a thyroid cancer mouse model with doxycycline (dox) inducible thyroid expression of *BRAF*V600E, [name] group (Memorial Sloan-Kettering Cancer Center (MSKCC)) demonstrated that dox treatment resulted in *BRAF*V600E overexpression, MAPK activation, development of PTC, and suppression of several thyroid specific genes, including *NIS* (Chakravarty et al., 2011). Withdrawal of dox to eliminate *BRAF*V600E expression resulted in suppression of MAPK activation and re-induction of thyroid gene expression, suggesting that oncogenic *BRAF* induced gene patterns can be reversed when *BRAF* activation of MAPK signaling is nullified. This genetic proof of concept was recapitulated with pharmacologic inhibition of *BRAF* activation: *BRAF*V600E was induced with one week of dox treatment and subsequently maintained while the animals were treated with the MEK inhibitor PD0325901 (PD901) or the selective oncogenic *BRAF* inhibitor PLX4720 (Plexxikon/Roche). Inhibition of *BRAF* signaling with either drug increased RAI incorporation over vehicle treatment, suggesting that inhibiting MAPK signaling with small molecule inhibitors can restore iodide uptake in thyroid tumors driven by a MAPK activating genetic alteration.

**Results of a pilot study evaluating the impact of MEK inhibition upon RAI incorporation and  $^{131}\text{I}$  efficacy:** We translated these preclinical findings into a pilot study evaluating the impact of the AstraZeneca MEK inhibitor selumetinib upon iodide uptake in patients with RAI-refractory thyroid cancers (Ho et al., 2013). A critical component of the study was the utilization of  $^{124}\text{I}$  PET/CT lesional dosimetry to precisely quantify drug-induced changes in iodide incorporation within specific lesions (Pentlow et al., 1996; Sgouros et al., 2004) and predict the  $^{131}\text{I}$  radiation dose that could be delivered to individual tumors.

Each of the 20 evaluable patients on the study had RAI-refractory disease as defined by one of the following criteria: 1) non-RAI-avid lesion/s on a diagnostic and/or post-therapy RAI scan, 2) RAI-avid lesion/s that remained stable or increased in size after RAI therapy, or 3) fluorodeoxyglucose (FDG)-avid lesion/s by PET scan. In order to optimize iodide uptake, human recombinant TSH (rhTSH or Thyrogen™ from Genzyme) was administered prior to each  $^{124}\text{I}$  PET, which was performed before and after treatment with selumetinib for 4 weeks. If the second  $^{124}\text{I}$  PET scan predicted that a lesional  $^{131}\text{I}$  dose of  $\geq 2,000$  cGy could be achieved,  $^{131}\text{I}$  was administered concomitantly with selumetinib. Of the 20 evaluable patients, 12 (60%) had new or increased  $^{124}\text{I}$  incorporation after selumetinib. For 8 (40%) patients, the second  $^{124}\text{I}$  PET scan predicted that the lesional absorbed  $^{131}\text{I}$  radiation dose would equal or exceed 2,000 cGy; these patients were continued on selumetinib and received therapeutic  $^{131}\text{I}$ . All 5 patients with *NRAS* MUT tumors on the study exceeded this dosimetry threshold and were treated with  $^{131}\text{I}$ .

By contrast, 4 out of 9 *BRAF* MUT patients had selumetinib-induced increases in  $^{124}\text{I}$  incorporation, but only one achieved the dose threshold to warrant  $^{131}\text{I}$  treatment. Two out of 3 *RET/PTC* and 1 out of 3 WT patients also had greater iodide incorporation on the second  $^{124}\text{I}$  PET scan, and one of each of those genotypes went on to be treated with  $^{131}\text{I}$ . These changes in iodide incorporation translated to clinical benefit as all 8 patients treated with  $^{131}\text{I}$  experienced reductions in tumor size. In total, there were 5 confirmed partial responses (cPRs) and 3 with stable disease (SD). Substantial decreases in serum thyroglobulin following RAI therapy were also achieved in all patients.

All evaluable patients completed the full course of selumetinib without dose reduction or delay. Toxicities attributed to selumetinib were Grade 1 or 2, and were consistent with adverse events reported in larger selumetinib studies (Hayes et al., 2012; Kirkwood et al., 2011), including fatigue (80%), maculopapular rash (70%), and acneiform rash (25%). Fourteen (70%) patients experienced Grade 1 elevations in liver transaminases possibly related to selumetinib, which reverted to baseline after drug discontinuation. One patient who was treated with  $^{131}\text{I}$  on study was diagnosed with myelodysplastic

syndrome more than 51 weeks later; the disease eventually transformed to acute leukemia. Prior to enrollment, this patient had received three courses of  $^{131}\text{I}$  (cumulative pre-study dose of 976.2 mCi) as well as 8640 cGy of external beam radiation for prostate cancer. Hence, this secondary malignancy was attributed to cumulative  $^{131}\text{I}$  and external beam radiation toxicities, and not to selumetinib.

***Selumetinib(ARRY 142886; AZD6244):*** Selumetinib is a potent, selective, noncompetitive inhibitor of MEK, licensed for development by AstraZeneca Pharmaceuticals from Array BioPharma. Selumetinib was discovered by Array Biopharma and had the designation ARRY 142886. Other laboratory code names used during the development of this molecule are AR00142886 and AR-142886-X (where X refers to a sequential lot number). Array BioPharma was responsible for the first-into-human study; the remainder of the clinical development program for oncology indications is the responsibility of AstraZeneca. AZD6244 has now been assigned the international nonproprietary name selumetinib.

Selumetinib inhibits the activity of isolated mitogen-activated protein kinase (MEK) to phosphorylate extracellular signal-regulated kinase (ERK) 2 in enzyme assays, with a concentration which resulted in 50% inhibition (IC50) of approximately 10 to 14 nM. In contrast, selumetinib was inactive, or only minimally active, against a panel of other kinases. N-desmethyl selumetinib (a pharmacologically active metabolite) was identified to be approximately 3- to 5-fold more active than the selumetinib parent compound. The amide metabolite is up to 50-fold less active than selumetinib, and is therefore unlikely to significantly contribute to biological activity.

As of 31 January 2014, approximately 1940 patients with cancer have received treatment with selumetinib, including approximately 750 patients in AZ-sponsored studies, 57 patients in the Array-sponsored Study ARRY-0401, 62 patients in the Merck-sponsored Study D1532C00028, and approximately 1070 patients in investigator- or collaborative group-sponsored studies. In addition, approximately 120 healthy volunteers have been exposed to selumetinib Hyd-Sulfate.

Selumetinib has been used as both monotherapy and in combination with other anti-cancer agents, in a variety of adult solid tumor settings (e.g., pancreatic cancer, colorectal cancer, melanoma and NSCLC), and pediatric cancer patients.

The formulation taken into the phase I clinical program by Array Biopharma was an extemporaneous preparation of an oral suspension of selumetinib as the free-base in an aqueous solution of sulphobutylether  $\beta$ -cyclodextrin (SBE-CD, Captisol®), referred to as the free-base suspension formulation (mix and drink).

The AstraZeneca phase II monotherapy clinical program also utilized this formulation. Subsequent formulation development resulted in a capsule formulation of selumetinib as the hydrogen sulphate salt (AZD6244 Hyd-Sulfate), which will be used in this study. The maximum tolerated dose (MTD) for the suspension formulation was determined to be 100 mg twice daily, whereas for the capsule, the MTD was determined to be 75 mg twice daily. The emerging safety and tolerability profile of the capsule formulation is broadly consistent with that of the suspension formulation, although a higher frequency of fatigue and nausea has been reported with the capsule formulation compared to the suspension formulation in the phase II monotherapy studies.

Two phase I studies (D1532C00005, D1532C00020) were performed with the Hyd-Sulfate formulation. Comparison of the frequencies from Study D1532C00005 and the AZ-sponsored phase II monotherapy studies described below shows that there are higher percentages of patients reporting the most frequent AEs such as fatigue, dermatitis acneiform, diarrhea, nausea and peripheral edema with the Hyd-Sulfate formulation. This may be due to the higher plasma exposures achieved with the capsule formulation, but may also be in part as a consequence of the more heavily pre-treated patient population in study D1532C00005 having lower tolerances to developing toxicity.

Two hundred and sixty nine (269) patients received selumetinib free base suspension 100 mg twice daily in 4 completed phase II monotherapy studies (D1532C00003, D1532C00008, D1532C00011, and D1532C00012).

- Rashes (including the preferred terms dermatitis acneiform, rash, rash maculopapular, rash macular, rash papular, acne, and folliculitis) were reported in approximately 70% of patients receiving treatment with selumetinib, and dermatitis acneiform was the most common AE term overall (54%). Other commonly reported AEs were diarrhea (49%), nausea (33%) and vomiting (24%). Adverse events of peripheral edema, periorbital edema, and facial edema were reported in 31%, 9%, and 4% of patients, respectively. The AEs of fatigue or asthenia were reported in approximately 30% of patients in this phase II population. Exertional dyspnea or dyspnea was reported in 13% of patients and, in individual studies, exertional dyspnea was reported at a higher incidence in the selumetinib groups than in the comparator chemotherapy groups.
- Serious AEs were reported in 24% of patients receiving selumetinib monotherapy. The most frequently reported serious AEs were vomiting (1.5%), diarrhea, erysipelas, and pulmonary embolism (in 1.1% patients each). Serious AEs of infections (bacterial sepsis, sepsis, infection, and bacterial arthritis) were reported in 2.2% of patients. The most frequently related reported treatment-related SAE was vomiting (3 patients).
- In Study D1532C00003, small increases in blood pressure were observed after 1 week on selumetinib, with mean increases of 7.4 mmHg (systolic, SBP) and 5.3 mmHg (diastolic, DBP) at Week 8, compared with mean increases of 1.1 mmHg (SBP) and 0.5 mmHg (DBP) in the temozolomide comparator arm. The AE of hypertension was reported in 18 patients (6.7%) receiving selumetinib in phase II monotherapy studies; 6 of these patients had hypertension at entry to the study, and a further 5 patients had documented risk factors for hypertension.
- Reversible asymptomatic reduction in left ventricular ejection fraction (LVEF) to below 55% has been reported in a small proportion of patients with advanced cancers in the monotherapy and randomized placebo controlled studies in combination with standard chemotherapies, with both formulations of selumetinib. In both placebo-controlled studies, no patient treated with selumetinib had severe LVEF impairment (< 35%) or symptomatic heart failure. Evidence of reversibility on continuing treatment with selumetinib has been demonstrated in some patients. LVEF scheduled assessments were only included in one phase II study (D1532C00003) and in the selumetinib group to evaluate a possible cardiac etiology of the peripheral edema reported in earlier studies. The median change in LVEF at Week 4 was 1.2 percentage points, and the individual change from baseline ranged from -20 to +19 percentage points. Adverse events of ejection fraction decreased, left ventricular dysfunction, or ventricular dysfunction were reported in a total of 5 patients (3.3%) receiving selumetinib (including 1 patient who had switched from temozolomide treatment after disease progression) versus 1 patient (1%) in the comparator group.
- Review of clinical laboratory parameters in phase II monotherapy studies identified a trend toward increased alanine aminotransferase (ALT) and aspartate aminotransferase (AST) levels after starting treatment with selumetinib. An increase in serum phosphate was observed in some patients after initiation of selumetinib, compared with patients randomized to comparator treatments. There was a trend toward a small mean decrease in albumin relative to the comparator. No other reports of selumetinib-related changes in laboratory parameters were considered to be of clinical relevance at this time. There was no evidence of myelosuppression or renal impairment.
- Adverse events related to visual function have been reported across the program with selumetinib. Most often there were no specific clinical findings reported from patients that underwent ophthalmological evaluation after reporting the AE of visual disturbance. AEs consistent with central serous retinopathy have been reported in a small number of patients receiving treatment with selumetinib, generally in combination with other anti-cancer agents.

- There have been reports of pneumonitis-type events in a small number of patients receiving treatment with selumetinib. An association with selumetinib has not been established.
- Weakness of neck extensor muscles in conjunction with creatine phosphokinase (CPK) increases (reversible on treatment interruption) have been reported in 3 out of 54 patients with uveal melanoma receiving selumetinib 75 mg twice daily in one non-AstraZeneca sponsored study. Increases in CPK levels have been recorded in a small number of patients receiving treatment with selumetinib. CPK elevations are present in some patients with muscle symptoms, although asymptomatic elevations have also been reported. A relationship between selumetinib and elevated CPK levels or myopathy has not been established.

In the pilot study described above where 20 metastatic, RAI-refractory thyroid cancer patients were treated with a 4 week course of selumetinib 75 mg twice daily (the Hyd-Sulfate formulation) to followed by  $^{131}\text{I}$  in a subset of patients (Ho et al., 2013), all events attributed to selumetinib were Grade 1 or 2, and included fatigue (80%), maculopapular rash (70%), acneiform rash (25%), elevation in AST (70%; all Grade 1), elevation in ALT (45%; all Grade 1), diarrhea (45%), nausea (40%), limb edema (30%), oral mucositis (35%), constipation (20%), hypoalbuminemia (15%), decreased white blood cell count (15%), face edema (10%), scalp pain (10%), decreased platelet count (1 patient; Grade 1), eye disorder (1 patient; Grade 1 consisting of visual halos and slight blurriness that resolved after therapy stopped), hypertension (1 patient; Grade 1), periorbital edema (1 patient; Grade 1), and vomiting (1 patient, Grade 1). One patient who was treated with  $^{131}\text{I}$  was subsequently diagnosed with myelodysplastic syndrome 51 weeks after  $^{131}\text{I}$  administration which subsequently evolved into acute leukemia (this was determined to be unrelated to selumetinib and likely related to cumulative RAI toxicity as well as previous external beam radiation therapy).

In the only other study to specifically investigate selumetinib in differentiated thyroid cancer patients (the phase II study of 100 mg bid selumetinib, previous mix-and-drink formulation) in 39 patients with RAI-refractory differentiated metastatic thyroid cancer. In these patients with RAI-refractory disease, common drug-related AEs included rash (77%), fatigue (49%), diarrhea (49%), and peripheral edema (36%). Grade 3 and 4 AEs were consistent with those across the selumetinib program and also included rash (18%), fatigue (8%), diarrhea (5%) and peripheral edema (5%). Twelve patients required dose reductions for reported AEs across the length of the study (the duration of treatment was greater than 16 weeks for 69% of patients). Six patients (15%) discontinued treatment due to adverse events.

Selumetinib is not mutagenic or clastogenic in vitro but produced increases in micronucleated, immature erythrocytes in mouse bone marrow micronucleus studies. Investigatory studies show that this is predominantly via an aneugenic mechanism which is consistent with disruption of normal spindle function as a consequence of the known pharmacological action of a MEK inhibitor. With selumetinib Hyd-Sulfate, a NOEL of 24 mg/kg/day (for 2 days) was established for induction of micronuclei, with plasma exposures significantly above those observed in cancer patients at the maximum tolerated dose of 75 mg twice daily. This suggests that selumetinib will have little potential to cause aneugenicity in dividing cell populations in patients at the proposed clinical dose.

In summary, selumetinib has been shown to have an acceptable profile of side effects, in an extensive safety database for a compound at this stage of development. Further details regarding the safety profile of selumetinib can be found in the Investigator Brochure.

*Rationale for evaluating the impact of selumetinib MEK inhibition upon  $^{131}\text{I}$  efficacy in RAI thyroid cancers:* We hypothesize that the limited efficacy of  $^{131}\text{I}$  alone for patients with structurally evident, RAI thyroid cancer is in part due to insufficient lesional  $^{131}\text{I}$  uptake and retention mediated by aberrant MAPK pathway inhibition. Pathway inhibition with selumetinib is predicted to increase expression of the thyroid-specific genes requisite to enhance  $^{131}\text{I}$  lesional delivery and efficacy. To test this hypothesis, we will perform a two-arm, randomized trial in which patients with RAI, recurrent/metastatic thyroid

cancer are randomized to  $^{131}\text{I}$  therapy in combination with approximately 4 weeks of therapy with either placebo or selumetinib. Hence, this study is appropriate only for patients with recurrent/metastatic thyroid cancer for whom  $^{131}\text{I}$  therapy is judged to be indicated. The primary clinical objective of the study will be to determine the overall response rate at 6 months following  $^{131}\text{I}$  therapy for each treatment arm. Secondary objectives will be to determine the best overall response, progression-free survival (PFS), changes in serum thyroglobulin levels, and safety/tolerability of each of the treatment arms.

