**NOTE: The Grade 4 or 5 Non-AER Reportable Events/Hospitalization Form is not being used for this study.**

**10.5 Other Required Reporting**

**10.51** Adverse events to be graded at each evaluation and pretreatment as specified in the Test Schedule (Section 4.0). The CTCAE v4.0 grading should be used unless an alternate grading method is indicated in the table below:

System Organ Class (SOC)	Adverse event/ Symptoms	Baseline	Each evaluation	Grading scale (if not CTCAE)
General disorders and administrations site conditions	Fatigue	X	X	
	Weight loss	X	X	
	Localized edema	X	X	
Gastrointestinal Disorders	Diarrhea	# of stools per day	X	
	Dyspnea	X	X	
	Nausea	X	X	
	Vomiting	X	X	
Eye Disorders	Blurred vision	X	X	
Vascular disorders	Hypertension	X	X	
Investigations	Alanine aminotransferase increase	X	X	
	Aspartate aminotransferase increase			
Skin and subcutaneous tissue disorders	Rash acneiform	X	X	
	Rash maculopapular	X	X	

10.52 Submit via appropriate Academic and Community Cancer Research United (ACCRU) Case Report Forms (i.e., paper or electronic, as applicable) the following AEs experienced by a patient and not specified in Section 10.5:

10.521 Grade 2 AEs deemed *possibly, probably, or definitely* related to the study treatment or procedure.

10.522 Grade 3 and 4 AEs regardless of attribution to the study treatment or procedure.

10.523 Grade 5 AEs (Deaths)

10.5231 Any death within 30 days of the patient's last study treatment or procedure regardless of attribution to the study treatment or procedure.

10.5232 Any death more than 30 days after the patient's last study treatment or procedure that is felt to be at least possibly treatment related must also be submitted as a Grade 5 AE, with a CTCAE type and attribution assigned.

10.53 Refer to the instructions in the Forms Packet (or electronic data entry screens, as applicable) regarding the submission of late occurring AEs following completion of the Active Monitoring Phase (i.e., compliance with Test Schedule in Section 4.0).

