#### 15.17 **Known potential toxicities:**

##### **Very Common Adverse Events, (>10%)**

Cardiovascular: Peripheral edema

Central nervous system: Fatigue, headache

Dermatologic: Rash acneiform, rash maculo-papular

Endocrine & metabolic: Creatine phosphokinase (CK) increased

Gastrointestinal: Diarrhea, nausea, vomiting, abdominal pain, constipation.

Respiratory: Exertional dyspnea

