### 16.3 Secondary Endpoints

The following endpoints will be compared between the 2 arms: best overall response, 6- month progression-free survival, changes in serum thyroglobulin levels, and adverse event rates between the 2 treatment arms. All patients who meet the eligibility criteria, sign the consent form, are randomized, and start any treatment will be considered evaluable for the endpoints below.

**Best overall response:** The best overall response will be compared between the two according to the criteria outlined in Section 11.0. This comparison will be done using a chi-square test. For a patient to be classified as a response, they need a partial or complete response that is confirmed at least 4 weeks later anytime during the study.

**Progression-Free Survival:** Progression-free survival (PFS) is defined as the time from study entry to the first of either disease progression or death from any cause, where disease progression will be determined based on criteria outlined in Section 11.0. PFS will be estimated using the Kaplan-Meier method, where the log-rank test will be used to compare the 2 treatment arms. Evidence of progression noted from the time of registration to within 6 months after  $^{131}\text{I}$  therapy may be disregarded as a progression event if the treating physician feels it is reasonable according to the rationale detailed in Section 16.2. The response assessment at 6 months for these patients will be based upon a comparison between the 6-month radiologic scan(s) and the baseline, pre-study radiologic scans. In addition, the 6-month PFS rate will also be compared between the arms.

**Serum Thyroglobulin Levels:** Changes in thyroglobulin will be assessed. The Wilcoxon Rank-Sum test will be used to compare the changes in thyroglobulin (pre-RAI and post-RAI) between the two treatment arms. (This analysis will not be possible for patients with detectable thyroglobulin antibodies.)

**Adverse events:** The maximum grade for each type of adverse event will be summarized using CTCAE version 4.0. The frequency and percentage of grade 3+ adverse events will be compared between the 2 treatment arms. Comparisons between arms will be made by using either the Chi-square or Fisher's Exact test.

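### Oral mucositis and constipation, both common and low-grade in the pilot, are missing from the Section 10.51 list, so the maximum-grade summary can understate them

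*Combined protocol and SAP*

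**What the plan says.** Section 10.51 sets the rule for solicited events: "Adverse events to be graded at each evaluation and pretreatment as specified in the Test Schedule (Section 4.0"). Its table names fatigue, weight loss, localized edema, diarrhea, dyspnea, nausea, vomiting, blurred vision, hypertension, ALT and AST increase, acneiform rash and maculopapular rash. Oral mucositis and constipation do not appear. The only edema term is "Localized edema".

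Section 10.52 governs submission of "the following AEs experienced by a patient and not specified in Section 10.5". It asks for three categories: grade 2 if at least possibly related, grades 3 and 4 whatever the attribution, and grade 5 (deaths). Grade 1 is not among them.

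Section 1.0 describes the pilot: 20 patients, selumetinib 75 mg twice daily in the same formulation, for 4 weeks. It states that "all events attributed to selumetinib were Grade 1 or 2" and gives the frequencies "limb edema (30%), oral mucositis (35%), constipation (20"%).

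For the analysis, Section 16.3 says that "The maximum grade for each type of adverse event will be summarized using CTCAE version 4.0", and separately that grade 3 or higher events will be compared between arms. Goal 2.24 makes safety and tolerability a secondary objective.

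**The concern.** The maximum-grade summary would mix two capture rules without saying so. For a listed term, every grade is recorded, with a baseline grade beside it. For an unlisted term, a patient whose worst grade is a non-serious 1 does not enter the data, and no baseline grade is called for.

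The pilot indicates that mucositis and constipation are expected on this regimen at exactly the grades where the rules differ. A reader comparing rows of the table would see them as rarer, relative to nausea or rash, than they were.

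The protocol itself treats both effects as relevant. Oral mucositis is among the expected events in Section 10.31. Appendix IV has a section on oral care and says treatment of stomatitis may be considered from grade 1, a grade Section 10.52 does not collect. Constipation is among the very common events in Section 15.17.

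**Working it through.** The plan states no figure for this point, so the check is a comparison of the sections followed by a range.

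**1. Pilot counts (Section 1.0, n = 20).**
- Oral mucositis: 0.35 × 20 = 7 patients
- Limb edema: 0.30 × 20 = 6 patients
- Constipation: 0.20 × 20 = 4 patients

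By frequency these rank 7th, 8th and 10th among the pilot events. The six above them (fatigue 80%, maculopapular rash 70%, AST 70%, ALT 45%, diarrhea 45%, nausea 40%) and the one at 9th (acneiform rash 25%) are all on the Section 10.51 list.

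**2. Match to the list.**

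| Pilot event | Section 10.51 term | What is submitted |
|---|---|---|
| Nausea, rash | Listed | All grades, plus baseline |
| Oral mucositis | None | Related grade 2, grade 3 and above, or serious |
| Constipation | None | Related grade 2, grade 3 and above, or serious |
| Limb edema | Localized edema, if coded there | All grades if so coded; otherwise as for mucositis |

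**3. Expected cases in the selumetinib arm.** Section 16.2 plans 28 evaluable patients per arm. At pilot rates:
- Mucositis: 28 × 0.35 = 9.8
- Constipation: 28 × 0.20 = 5.6
- Sum: 15.4 events (one patient may have both)

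**4. Cases submitted.** Let *s* be the share of affected patients whose worst grade is 1. The documents do not give it, so it is varied over its whole range. Assuming that no grade 1 case is serious and that every grade 2 case is judged at least possibly related, cases submitted = expected cases × (1 − *s*).

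| *s* (assumed) | Mucositis submitted (rate) | Constipation submitted (rate) |
|---|---|---|
| 0 | 9.8 (35%) | 5.6 (20%) |
| 0.5 | 4.9 (17.5%) | 2.8 (10%) |
| 1 | 0 (0%) | 0 (0%) |

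Grade 2 cases judged unrelated would lower these counts further.

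**5. Limb edema.** Expected cases are 28 × 0.30 = 8.4. None is lost if it is recorded as localized edema. If it is coded under a separate, unlisted term, between 0 and 8.4 are lost, depending again on *s*. The protocol does not settle which: Section 10.31 uses site-specific terms for the face and trunk, Section 10.12 treats each CTCAE term as a distinct event, and Section 15.17 has "Cardiovascular: Peripheral edema".

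**6. Planned comparison.** Section 16.3 compares grade 3 or higher events. Section 10.522 collects grades 3 and 4 whatever the attribution, and Section 10.523 covers deaths. Adding terms to the list would not alter this comparison.

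**The case against.** The strongest reply is that tiered collection is deliberate, stated openly in Section 10.52, and applied identically to both blinded arms. Related grade 2 mucositis and constipation are captured. What is missed is mild, and it affects only a descriptive summary of a secondary goal. Nor is the list meant to be complete: headache, CK increase and abdominal pain are also above 10% in Section 15.17 and unlisted, and that section puts stomatitis at only 1 to <10%. All of this stands, and it is why the point is minor. It does not remove the uneven capture, because Section 16.3 does not tell the reader that its rows follow different rules. The 35% pilot rate, on the dose and formulation used here, is also a good reason to want an accurate mucositis figure.

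Three stronger readings are tempting and are not supported.

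- *That three pilot toxicities are omitted.* Localized edema is listed and can hold limb edema at any grade. What remains is an ambiguity of coding.
- *That grade 1 cases can never be submitted.* Section 10.41 requires expedited reporting of a serious grade 1 event with hospitalization of at least 24 hours, and Section 10.11 requires expedited events to be reported routinely as well.
- *That the trial loses power to show a tolerability difference.* Section 16.3 plans no all-grade test. Any such power figure would need an assumed placebo rate, significance level and grade split, none of which the documents give for that test.

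It would also be wrong to infer that the existing entries are ill-chosen. Vomiting, seen in one pilot patient, was reported in 24% of the 269 phase II patients on the suspension formulation.

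**Conclusion.** The point holds for oral mucositis and constipation. Both are absent from Section 10.51, and Section 10.52 does not call for their non-serious grade 1 cases or unrelated grade 2 cases. The maximum-grade summary can therefore understate them relative to listed terms.

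The size cannot be fixed from the documents. At pilot rates about 9.8 and 5.6 cases are expected among 28 selumetinib patients, and anywhere from none to all of them could go unsubmitted. This rests on pilot rates from only 20 patients carrying over to this trial, where time on treatment may extend to 8 weeks.

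For limb edema the finding is only that the recording term is unstated. Severity is minor: the primary endpoint and the planned adverse event comparison are untouched.

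**What to change.** Add *Mucositis oral* and *Constipation* to the Section 10.51 table, marked for baseline and each evaluation, and to the matching Baseline Adverse Event and Nadir/Adverse Event forms in Section 18.1. State in Section 10.51 the term under which limb edema is to be recorded.

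If the list is left as it is, Section 16.3 should say that summaries of unlisted events exclude non-serious grade 1 cases and unrelated grade 2 cases.

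The cost is two more lines on existing forms and slightly more data entry. No visit, test or treatment rule changes.
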